12.1.1 Sample Size/Accrual Rate

We estimate an annual enrollment of 16-20 patients based on the existing referral patterns and proton slot availability over 3 years of active accrual. Since protocol enrollment began in August 2011, the accrual rate has been about 15 patients per year, thus increasing the accrual goal from 58 to 64 post-mastectomy patients is projected to take another 4-5 months. Based on existing referral patterns of patients following breast-conserving surgery, we estimate the intact breast cohort will require 5-6 months to enroll the cohort goal of 32 patients. All patients will be followed for an additional 5 years to allow for the assessment of late toxicities and progression-free survival.

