12.1 Study Design/Endpoints

This is a pilot study substituting proton radiation for photon radiation, seeking to show the feasibility of proton radiation and to assess the rate of acute, sub-acute and late toxicities during and after proton radiation to the left chest wall and regional lymphatics. It is anticipated that patients undergoing proton radiation will not have increased toxicity compared to patients who have historically undergone photon radiation.

Proton radiation will be considered to be feasible as adjuvant treatment for invasive breast carcinoma in each cohort following surgery if the rate of grade 3 or higher radiation pneumonitis within 3 months of treatment were no more than 5%, within the range associated with conventional techniques of adjuvant radiation. In addition to radiation pneumonitis, the feasibility of proton radiation will also be compromised by any grade 4 effect occurring within 3 months of treatment, as well as skin toxicity and pericarditis. If 2 or more of the initial 12

CONFIDENTIAL

This document is confidential. Do not disclose or use except as authorized.

patients were to experience grade 3 or higher radiation pneumonitis or any grade 4 toxicity within 3 months of finishing radiation, accrual to a cohort will not continue further. The probability of stopping early is only 12% if the underlying rate of grade 3 or higher radiation pneumonitis or any grade 4 toxicity were truly 5%. Otherwise, the cohort will proceed to enroll a total of 26 patients and declare the feasibility of proton radiation if no more than 2 of them were to experience grade 3 or higher radiation pneumonitis or any grade 4 toxicity within 3 months after treatment. The two-stage design provides 81% power to accept that proton radiation is associated with a 5% rate of grade 3 or higher radiation pneumonitis or any grade 4 toxicity in a treated cohort. However, the probability is only 20% for declaring the feasibility of proton radiation if the underlying rate grade 3 or higher radiation pneumonitis or any grade 4 toxicity were truly 15%.

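### At the projected 5-6 month accrual, all 32 intact-breast patients are enrolled before the first 12 have complete 3-month outcomes, so the stage-1 rule loses most of its limit on exposure

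*Combined protocol and SAP*

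**What the plan says.** Section 12.1 sets a two-stage rule for each cohort. It begins "If 2 or more of the initial 12" and turns on grade 3 or higher pneumonitis or any grade 4 "toxicity within 3 months of finishing radiation, accrual to a cohort will not continue further". If the rule is not met, "the cohort will proceed to enroll a total of 26 patients and declare the feasibility of proton radiation if no more than 2 of them" have an event. The operating characteristics follow: "The probability of stopping early is only 12% if the underlying rate" is 5%, "The two-stage design provides 81% power" at 5%, and a 20% chance of declaring feasibility at a true rate of 15%.

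Section 12.1.1 gives the pace. For post-mastectomy patients since August 2011, "the accrual rate has been about 15 patients per year". For the new cohort, "we estimate the intact breast cohort will require 5-6 months to enroll the cohort goal of 32 patients", on the basis of referral patterns after breast-conserving surgery.

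No section describes a pause after patient 12, or says whether events are acted on as they occur or only once all 12 have been followed for 3 months. The Study Calendar (Section 7) places visits at 4 weeks, 2 months and 6 months after treatment, with none at 3 months.

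**The concern.** A stage-1 look limits exposure only if its data are available while most of the cohort is still to be enrolled. Here the outcome takes the length of radiation plus 3 months to mature, while the whole cohort is projected to enrol in 5-6 months. The plan's stopping rule and its accrual projection therefore do not fit together. This is the only numerical stopping rule in the trial, and the intact-breast group is a new population for it. If the technique were too toxic in that group, the rule is what should keep the number treated near 12.

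**Working it through.** **1. The plan's own figures.** Exact binomial, 12 patients then 14 more, stop at 2 or more of 12, feasible at 2 or fewer of 26.

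- Early stop at 5%: 1 − 0.95^12 − 12 × 0.05 × 0.95^11 = 11.8% (stated 12%).
- Declared feasible: sum over x = 0, 1 of P(X1 = x) × P(X2 ≤ 2 − x), with X1 on 12 and X2 on 14 patients. This gives 81.3% at 5% (stated 81%) and 20.0% at 15% (stated 20%).
- Early stop at 15%: 1 − 0.85^12 − 12 × 0.15 × 0.85^11 = 55.7%. Expected enrolment if the look works as designed: 12 + 14 × (1 − 0.557) = 18.2 of 26.

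All three stated figures reproduce.

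**2. Radiation duration (assumption).** Section 5.2.4 gives 45-50.4 Gy(RBE), typically 5 days a week, but no fraction size. Assuming 1.8-2.0 Gy per fraction, the range is 45/2.0/5 = 4.5 weeks to 50.4/1.8/5 = 5.6 weeks, or 1.03-1.29 months.

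**3. Timeline at the projected pace.** With uniform accrual over T months, patient k enters at k/32 × T. Stage-1 data are complete at 12/32 × T + radiation + 3.

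| | T = 5 months | T = 6 months |
|---|---|---|
| 12th entry | 1.88 | 2.25 |
| 26th entry | 4.06 | 4.88 |
| 32nd entry | 5.0 | 6.0 |
| Stage-1 data complete, 4.5-5.6 weeks of radiation | 5.91-6.16 | 6.28-6.54 |
| Stage-1 data complete, zero radiation time | 4.88 | 5.25 |

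So all 32 are enrolled first under the assumed duration. For this the course must exceed about 0.5 week at T = 5 ((5 − 4.875) months) or about 3.3 weeks at T = 6 ((6 − 5.25) months). That all 26 design patients are enrolled first needs no assumption about duration.

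**4. Ascertainment.** The 2-month visit has a window of 3 weeks either way, so its latest date is about week 8 + 3 = 11, still short of 3 months. If status were confirmed only at the 6-month visit, even on its nominal date, stage-1 data would be complete at 1.88 + 1.03 + 6 = 8.9 to 2.25 + 1.29 + 6 = 9.5 months.

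**5. Can early events trigger the rule?** Yes, because a second event settles it before all 12 are followed up. I simulated a true 15% rate with T = 5-6 months and 4.5-5.6 weeks of radiation. The results are conditional on the rule being met, and they assume each event is known and acted on at once.

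| Assumed event timing | Trigger before 26th entry | Trigger before 32nd entry | Median enrolled at trigger |
|---|---|---|---|
| Uniform from start of radiation to 3 months after | 67-86% | 89-99% | 19-22 |
| Uniform from 1 to 3 months after radiation | 27-72% | 77-98% | 24-28 |

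Placing the first patient at month zero, rather than after one accrual interval, lowers the top of the median range to about 27.

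**6. Dependence on pace.** 32 patients in 5-6 months is 32/6 × 12 = 64 to 32/5 × 12 = 77 a year. At 15 a year, the 4.03-4.29 months between the 12th entry and the look admit (4.03 to 4.29) × 15/12 = 5.0-5.4, or about 5 extra patients.

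**7. With a full hold.** Duration becomes T + 4.03 to T + 4.29, that is 9.0-10.3 months.

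**The case against.** A reader might infer that the rule cannot act at all in this cohort. The documents do not support that. The rule needs two events, not 12 completed follow-ups. Toxicity is assessed weekly during radiation and at each follow-up visit, serious events up to 30 days after the last dose are reported within 24 hours (Section 9.5.1), and a data and safety monitoring committee reviews toxicity and accrual (Section 10.2). Step 5 shows that most stops could come before the 32nd entry. This stands, with two limits. Those stops come late, and the 24-hour reporting ends 30 days after treatment, although the outcome window runs to 3 months.

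A reader might also infer that the operating characteristics fail, and that a single-stage rule of 2 or fewer of 26 (86% and 23%) describes the trial. That would require stage 1 to be discarded, which no section says. Applied to the first 12, even after accrual has finished, the rule keeps 81% and 20%.

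Stage 2 is worded as conditional on stage 1, so a hold can be read into Section 12.1. That is a fair reading, but a hold of about 4 months does not fit a 5-6 month projection, so one of the two statements must change.

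Finally, the difficulty exists only at the projected pace. That is true. It is nevertheless the sponsor's own projection, and it rests on a different referral population. For the same reason the post-mastectomy rate should not be carried over to predict how long this cohort will take.

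**Conclusion.** The point holds in a limited form. At the projected pace the stage-1 rule cannot be fully evaluated before accrual ends. It loses most of its limit on exposure: at a true 15% rate about 19-28 patients would typically be enrolled at the trigger rather than 12. The comparison with all 32 enrolled rests on uniform accrual and an assumed 4.5-5.6 weeks of radiation. The comparison with the 26th entry holds for any duration. The enrolment medians rest on assumed event timings and on immediate action. The error rates in Section 12.1 are not in question. If accrual runs nearer 15 a year, about 5 extra patients enter before the look and the rule largely works.

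**What to change.** In Section 12.1, state three things:

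1. A cohort closes to accrual as soon as a second qualifying event among its first 12 patients is confirmed.
2. Entry beyond patient 12, or beyond a stated small overrun, waits until the 3-month status of the first 12 is known.
3. How that status is obtained, for example by a contact at 3 months, since scheduled visits fall at 2 and 6 months.

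In Section 12.1.1, restate the intact-breast duration to agree: about 9-10 months at the projected pace with a full hold.

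The cost is wording, plus a pause of about 4 months in that cohort if accrual is as fast as projected. The 12%, 81% and 20% do not change.

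In the same edit, reconcile Section 6.3, which accepts up to 3 events among 26, with Section 12.1, which accepts up to 2. With the same stage-1 rule, up to 3 gives 86.9% at 5% and 31.7% at 15%; only up to 2 reproduces the stated 81% and 20%.

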12.1.2 Stratification Factors

Protocol accrual will be stratified by proton technique (3D conformal and IMPT) and by surgery procedure (mastectomy and breast-conserving). Post-mastectomy patients will be enrolled in sequential cohorts, while patients with intact breast will only be treated with IMPT. In general, primary and secondary endpoints will be analyzed separately for each proton cohort.

12.2 Analysis of Secondary Endpoints

Secondary endpoints of this study will be analyzed as follows:

- 12.2.1 Exact binomial methods will be used to construct 95% confidence intervals for estimating the rates of acute, sub-acute and late toxicities during and after proton radiation to the left chest wall and regional draining lymphatics. The precision provided by a sample size of 26 patients is associated with a maximum half-width of 20%, but the 95% confidence intervals will be narrower in practice, as the observed toxicity rates are expected to be generally low. The same methods will also be used to analyze the post-radiation outcomes of breast reconstruction, including the rates of implant complication, contracture, infection, unplanned cosmetic surgeries.
- 12.2.2 Progression-free survival is defined as the duration from the start of radiation to the date of objective disease progression or death due to any cause, whichever is earlier. Progression-free survival will be estimated using Kaplan-Meier methodology. The 5-year

CONFIDENTIAL

This document is confidential. Do not disclose or use except as authorized.

progression-free survival rate will be reported and a 95% confidence interval for this rate will be calculated using Greenwood's formula. Patients who do not experience a progression and are still alive will be censored at their date of last contact.

- 12.2.3 Data from the strain echocardiogram will be analyzed for each parameter, including myocardial velocity, strain, strain rate and torsion. ANOVA methods will be used to analyze the pre- and two post-radiation measurements, using linear contrasts to test the significance of cardiac function changes over time. Fixed effects may be incorporated to explore subgroup differences defined by patient and treatment factors, for example, dose level.

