12. STATISTICAL CONSIDERATIONS

We propose to enroll a total of 96 patients in three cohorts following the study design indicated in 12.1 to evaluate independently the feasibility of intensity modulated proton therapy (IMPT) and 3D conformal protons following mastectomy or breast-conserving surgery. The separate cohorts will ensure adequate patient numbers for achieving reasonable precision in the assessment of acute, sub-acute and late toxicities associated with each proton technique in the specific population. The accrual goal includes 20% inflation to account for patients unevaluable or lost to follow-up so that adequate precision is maintained for longer-term endpoints. The target accrual has been adjusted based on the observed data among mastectomy patients with at least 6 months follow-up, including the completeness of strain echocardiogram testing.

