12.3 Reporting and Exclusions

- 12.5.1 **Evaluation of toxicity.** All participants will be evaluable for toxicity from the time of their first treatment.
- 12.5.2 **Evaluation of response.** Although patients will not have measurable disease at the time of treatment and therefore response is not an endpoint of this study, all patients will be followed for disease recurrence.

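### Section 12.2.1 plans late toxicity and reconstruction rates as crude binomial proportions with no time point, denominator or censoring rule, so incomplete 5-year follow-up would distort them

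*Combined protocol and SAP*

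**What the plan says.** Section 12.2.1: "Exact binomial methods will be used to construct 95% confidence intervals for estimating the rates of acute, sub-acute and late toxicities". It then adds: "The same methods will also be used to analyze the post-radiation outcomes of breast reconstruction", naming implant complication, contracture, infection and unplanned cosmetic surgery. Its only precision statement is "The precision provided by a sample size of 26 patients is associated with a maximum half-width of 20" per cent.

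Section 12 allows for missing patients through accrual: "The accrual goal includes 20% inflation to account for patients unevaluable or lost to follow-up so that adequate precision is maintained for longer-term endpoints". The total is set by "We propose to enroll a total of 96 patients in three cohorts", and Section 12.1.1 refers to "the cohort goal of 32 patients" for the intact-breast cohort.

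On who is counted, Section 12.3 says "All participants will be evaluable for toxicity from the time of their first treatment". Section 8.1.1 says much the same of everyone who receives at least one dose. Neither sets a minimum follow-up.

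Sections 5.5 and 12.1.1 set 5 years of follow-up, ending earlier at death. Section 12.2.2 analyses progression-free survival by Kaplan-Meier and censors at last contact. No such rule is given for late toxicity or reconstruction outcomes.

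**The concern.** A binomial proportion needs each patient's status at a defined time. For events that build up over 5 years, a patient last seen at month 6 has no known 5-year status. The plan does not say whether that patient counts as event-free, is dropped, or contributes only the time observed. Enrolling more patients restores precision but does not remove the bias from unequal follow-up.

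Section 1.3.1 says the secondary endpoints will form the basis for designing future studies, and reconstruction is central to the rationale in Sections 1.2 and 2.3. A late rate with no stated time or denominator is hard to reuse. It is also hard to compare between the post-mastectomy cohorts, which are enrolled in sequence (Section 12.1.2) and so may differ in length of follow-up at any analysis.

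**Working it through.** **The plan's own figures reproduce.** The largest half-width of the exact (Clopper-Pearson) 95% interval with n = 26 is 20.07%, against 20% stated. Accrual: 26 × 1.2 = 31.2, rounded up to 32, and 3 × 32 = 96. The six extra patients are 6/32 = 18.75% of a cohort.

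**Inputs.** From the documents: 5-year horizon, 32 per cohort, exact binomial interval. Assumed, because the documents give no figures: true 5-year risk F from 5% to 40%, constant event hazard, and 20% loss by year 5 independent of the event. The 20% borrows the size of the accrual inflation for illustration.

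**Formulas.** λ = −ln(1 − F)/5 and μ = −ln(0.8)/5 = 0.0446 per year.

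- All treated, losses spread over 5 years: p = λ/(λ + μ) × [1 − exp(−5(λ + μ))].
- All treated, losses uniform over year 1: p = 0.8F + 0.2 × [1 − (1 − e^(−λ))/λ].
- Events plus completers, spread losses: p/(p + 0.8(1 − F)), with p from the first line.

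**Worked case, F = 30%.** λ = 0.0713.

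- Spread: (0.0713/0.1160) × (1 − 0.56) = 27.1%.
- Year 1: 0.240 + 0.2 × 0.0348 = 24.7%.
- Events plus completers: 0.2707/(0.2707 + 0.56) = 32.6%.

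**Coverage.** This is the binomial(32, p) probability that the exact 95% interval around the all-treated rate contains F.

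| True 5-year rate | All treated, spread | All treated, year 1 | Events + completers | Coverage, spread | Coverage, year 1 |
|---|---|---|---|---|---|
| 5% | 4.5% | 4.1% | 5.6% | 99% | 99% |
| 10% | 9.0% | 8.2% | 11.1% | 99% | >99% |
| 20% | 18.0% | 16.4% | 22.0% | 98% | 97% |
| 30% | 27.1% | 24.7% | 32.6% | 95% | 92% |
| 40% | 36.2% | 33.0% | 43.0% | 93% | 87% |

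With no loss, coverage at a true 40% is 95.4%. With year-1 losses at 40% the misses are one-sided: the interval lies wholly below the truth in 12.3% of cohorts and wholly above it in 0.2%.

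**Time-to-event estimate.** In 8,000 simulated cohorts of 32 with a true 20% and spread losses, one minus Kaplan-Meier averaged 20.0%. The crude versions averaged 18.0% (all treated) and 22.0% (events plus completers). The standard deviation was 7.4 points, against 6.7 for the all-treated rate.

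**The case against.** Several stronger readings are tempting, and the documents do not support them.

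- **That the rates and intervals are biased as planned.** The size and direction depend on follow-up that has not yet happened and on a denominator the plan does not clearly fix. A rate among patients whose inclusion does not depend on the event would be unbiased under non-informative loss.
- **That the plan favours protons by understating harm.** Section 12.3 says who is evaluable and from when; it does not say that a lost patient counts as event-free at 5 years. Stating precision on 26 rather than 32 suggests that fewer than all enrolled patients were expected in the longer-term rates. Counting all treated patients is the literal reading, but not the only one.
- **That the plan expects 20% loss.** The 20% is an accrual inflation that pools unevaluable and lost patients. It is neither a forecast nor a cap.
- **That the distortion is large.** Section 12.2.1 expects toxicity rates to be generally low. At true rates of 5% to 20% the all-treated rate is off by about 0.5 to 4 points, while an observed 6/32 has an exact interval of 7.2% to 36.4%. No document gives 30% or 40% for a late outcome.
- **That the n = 32 figures apply to reconstruction.** Reconstruction is optional (Section 3.1.2) and one cohort has intact breasts, so the at-risk group is an unstated subset.

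The endpoints are also descriptive, and using Kaplan-Meier only for progression-free survival is not a contradiction. All of this limits the size of the point. What stands is that the plan names a method that cannot handle partial follow-up, for endpoints where it makes allowance for such follow-up.

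**Conclusion.** The point holds as a conditional one. For late toxicity and reconstruction outcomes the method, time point, denominator and censoring rule are not adequate to incomplete 5-year follow-up. Under a constant hazard and 20% independent loss, the all-treated rate is about 10% too low in relative terms when losses are spread, and up to 18% too low when they fall in year 1. Counting events plus completers makes it about 7% to 11% too high with spread losses. Interval coverage around the all-treated rate falls below 95% only at the higher rates examined: 30% with year-1 losses, and 40% with either loss pattern. Informative loss or competing deaths could change these sizes, and the documents give no figures for either. The 3-month feasibility decision is not affected. The change is worth making because these rates are meant for later design work and the remedy is cheap.

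**What to change.** Keep exact binomial intervals for acute and 3-month toxicities. For late toxicities and reconstruction outcomes:

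- Report cumulative incidence at stated times, such as 1, 2 and 5 years, with 95% intervals.
- Censor at the last toxicity assessment and treat death as a competing event.
- Restrict reconstruction outcomes to reconstructed patients, and state how many there are.
- Where no events occur, give an exact binomial upper limit based on patients followed to that time. For example, 0/26 gives 1 − 0.025^(1/26) = 13.2%. This case matters: at a true 5% with spread losses, (1 − 0.0449)^32 = 23% of cohorts of 32 would show no events, and log-log intervals are then undefined.

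The cost is revised SAP wording and routine software. The intervals will be slightly wider. Onset times will be known only to within the visit windows, which the study calendar sets at ±6 months for the 6-month and annual visits. The listed forms do not show onset-date fields, so the team should confirm that onset and last-assessment dates are recorded.

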7. STUDY CALENDAR

Baseline evaluations are to be conducted within 6-weeks prior to start of protocol therapy. Scans must be done ≤ 12 weeks prior to the start of chemotherapy if delivered or radiation therapy if no chemotherapy is delivered. In the event that the participant's clinical condition is deteriorating, laboratory evaluations should be repeated within 48 hours.

Tests and Observations	Pre-study	During Radiation	Follow Up (1)
Informed Consent and registration	X		
Pathology Review (DF/HCC)	X		
Medical History	X		
Physical Exam	X		X
Echocardiogram (2)	X		X(2)
Imaging	X (3)		As clinically indicated
Toxicity/AE Assessment		X weekly	X
Data Sheets			X (4)
Labs (5)	X		X
Optional Photography	X	X	X

Notes:

(1) Follow up schedule is at 4 weeks and 2 months, and 6 months after treatment, then at 12 months and annually to five years after treatment. Labs are only collected at the first two follow up visits (4 weeks and 2 months). Visit window for follow up is +/- 3 weeks for the 4week and 8 week follow up visits, then +/- 6months for the 6month and annual visits.

(2) Echocardiogram including Strain echocardiogram will be performed for all patients. Echocardiogram data will be collected prior to radiation therapy (or within first week of treatment), at 4 weeks after completion of radiation therapy, and 2 months after radiation therapy. Conventional two-dimensional (2D) and Doppler echocardiography will be obtained in standard views. Tissue Doppler imaging will be acquired using standard views. Imaging parameters will be optimized and the frame rate will be set greater than 150 frames/sec for acquisition of tissue Doppler imaging. Echocardiographic loops of at least 3 beats will be recorded. Echocardiograms will be read in the conventional manner and reported in the subject's medical record. TDI-derived parameters, such as myocardial velocities, strain, strain rate and torsion, will be analyzed offline using customized computer software (EchoPac, GE Healthcare, Milwaukee, WI).

(3) Diagnostic imaging required pre-study:

- Baseline mammography prior to surgery
- For patients with lymphatic involvement Computed Tomography (CT) scan of the chest, CT of the abdomen, and bone scan and/or Positron Emission Tomography (PET)/CT scan are required. For patients with low burden nodal disease, these scans are not required.

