8.1.2 Progression-Free Survival

Tumor control is not the primary objective of this Pilot Study. Participants will be followed for toxicities and Progression-Free Survival (PFS), which is defined as the duration of time from start of treatment to time of objective disease progression.

Progressive disease will be defined as the appearance of one or more new lesions. Disease progression will be assessed at follow up by clinical exam, and may be further assessed by imaging as determined by the treating investigator.

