9.5 Sponsor Notification by Investigator

9.5.1 Serious Adverse Event Reporting Requirements

All events meeting the criteria for Serious Adverse Event (see Section 11.2.2) that occur after the initial dose of study treatment, during treatment, or within 30 days of the last dose of treatment must be reported as serious adverse events.

The participating investigator must report each serious adverse event, regardless attribution, to the Principal Investigator (or Protocol Chair) within 24 hours of learning of the occurrence. In the event that the participating investigator does not become aware of the serious adverse event immediately (e.g., participant sought treatment elsewhere), the participating investigator is to report the event within 24 hours after learning of it and document the time of

CONFIDENTIAL

This document is confidential. Do not disclose or use except as authorized.

Eligibility Checklist	Complete prior to registration with QACT
On Study Form	Within 14 days of registration
Baseline Assessment Form	Within 14 days of registration
Treatment Form	Within 10 days of the last day of study treatment
Toxicity/Adverse Event Report Form	Weekly during study treatment; Within 10 days of protocol-defined follow up
Lab Form	Within 14 days of protocol required labs
Measurement/Response Form	Within 14 days of registration; within 10 days of protocol-defined follow up
Off Treatment/Off Study Form	Within 14 days of completing treatment or being taken off study for any reason
Follow up/Survival Form	Within 14 days of the protocol defined follow up visit date or call

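### Censoring progression-free survival at last contact, which may be a call, can credit unexamined time as progression-free and can raise the 5-year rate by a few points

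*Combined protocol and SAP*

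**What the plan says.** Section 12.2.2 runs progression-free survival (PFS) from the start of radiation to "the date of objective disease progression or death due to any cause, whichever is earlier". It adds that "Progression-free survival will be estimated using Kaplan-Meier methodology", with the 5-year rate reported and a Greenwood 95% confidence interval. Its censoring rule is: "Patients who do not experience a progression and are still alive will be censored at their date of last contact".

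Section 8.1.2 describes how progression is found: "Disease progression will be assessed at follow up by clinical exam, and may be further assessed by imaging as determined by the treating investigator". It defines PFS as "the duration of time from start of treatment to time of objective disease progression", without mentioning death, so the two definitions also need to be aligned.

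The table of form due dates just before Section 10.2 gives the deadline for the Follow up/Survival Form as "Within 14 days of the protocol defined follow up visit date or call". The study calendar (Section 7) marks a physical exam at follow-up, with visits at 4 weeks, 2 months and 6 months, "then at 12 months and annually to five years after treatment".

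No text requires the last contact to include a disease evaluation, and no rule covers missed exams.

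**The concern.** The event is detected by exam, but the censoring date need not be an exam date. Take a patient last examined at year 2 and reached by phone, alive, at year 5. Under the rule as written she stays in the risk set as progression-free for all five years, exactly like a patient examined every year. If she progressed in between and the call did not bring it out, a failure is lost and the curve stays too high. She also counts as fully at risk in the Greenwood variance for three years in which nobody looked.

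After month 12 the visits are annual, so one missed visit leaves two years between nominal exam dates. Describing the 5-year PFS rate is a stated objective (1.3.2), and the secondary results are meant to inform future studies. Two analysts could also report different rates from the same data, depending on what each took to be a contact.

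**Working it through.** **Plan's own figure.** There is none to reproduce: the documents give no expected PFS rate, event count or PFS precision.

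**Inputs from the documents.** 96 patients in three cohorts (Section 12), 32 of them in the intact-breast cohort and 64 post-mastectomy (12.1.1); 26 patients per cohort in the two-stage design (12.1); endpoints generally analysed by cohort (12.1.2).

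**Inputs assumed.** True 5-year PFS of 70, 80 or 90% with constant hazard; the fraction q of patients who stop exams but are still reached by call; how long the calls go on; and the share d of progressions that calls detect.

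**1. Closed form for a severe case.** Let call-only patients have their last exam at 0.5, 1, 2 or 3 years with equal chance, and be called to year 5. Let 90% of first events be progressions. Everyone is then followed to year 5, so

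bias = q × 0.9 × (1 − d) × mean of [S(last exam) − S(5)].

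At a true rate of 80%, the hazard is −ln(0.8)/5 = 0.0446 per year, and S = 0.978, 0.956, 0.915 and 0.875 at the four times. The mean of S − 0.8 is 0.131.

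- q = 10%, d = 0: 0.1 × 0.9 × 0.131 = 1.2 points
- q = 20%, d = 0: 2.4 points, so 82.4% is reported
- q = 20%, d = 0.5: 1.2 points
- any q, d = 1: 0 points

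**2. Wider range.** Large-sample Kaplan-Meier simulation: 400,000 patients per scenario, exams stopping uniformly between 0.5 and 5 years, calls continuing for the stated time (contact capped at 5.5 years), all events treated alike.

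| True 5-year PFS | Call-only share | Calls continue | Reported, calls detect none | Reported, calls detect half |
|---|---|---|---|---|
| 80% | 10% | 1 year | 80.3% | 80.2% |
| 80% | 30% | 1 year | 81.1% | 80.6% |
| 80% | 30% | 2 years | 81.9% | 80.9% |
| 80% | 50% | 5 years | 84.3% | 82.2% |
| 70% | 50% | 5 years | 76.2% | not run |
| 90% | 50% | 5 years | 92.2% | not run |

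When calls detect everything, the reported rate at 80% is about 80.0%. Censoring at the last exam, with only events up to that exam counted, returns the true rate within simulation error in every scenario.

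**3. Interval width.** In the case of step 1 with q = 20% and d = 0, last-contact censoring gives a standard error of √(0.824 × 0.176/32) = 0.067. Under last-exam censoring, the fraction still examined is 1, 0.95, 0.90, 0.85 and 0.80 over 0–0.5, 0.5–1, 1–2, 2–3 and 3–5 years. Summing [1/S(end) − 1/S(start)]/fraction gives 0.0226 + 0.0243 + 0.0530 + 0.0587 + 0.1334 = 0.2920. The standard error is 0.8 × √(0.2920/32) = 0.076. The first is about 12% smaller. Simulated cohorts of 32 gave 0.068 and 0.077.

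**4. Yardstick.** The approximate 95% half-width at 80% is 1.96 × √(0.8 × 0.2/32) = 13.9 points for 32 patients, and 15.4 points for 26.

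**5. Risk in a half-made fix.** Suppose event-free patients are censored at last exam, but events learned of later by call are still counted. With 30% call-only for 1 or 2 years, a true 80% is then reported as 78.9% or 78.2% if calls detect every event, and as 79.5% or 79.0% if they detect half. If only later deaths are counted, the effect is small. In the case of step 1 with q = 20% and deaths as 10% of first events, the added cumulative hazard is about 0.0446 × 0.1 × (0.05/0.95 × 0.5 + 0.10/0.90 × 1 + 0.15/0.85 × 1 + 0.20/0.80 × 2) = 0.0036. That lowers 80% by about 0.3 points.

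**The case against.** The planned contact is an exam. Section 7 marks a physical exam at follow-up through year 5, no telephone visit is scheduled, and Section 12.3 says all patients will be followed for recurrence. If the calendar is kept, last contact and last exam coincide. The call route rests on two words in a form-deadline table. The continued contact in Section 9.1 concerns ongoing adverse events and adds little. The endpoint is descriptive, with no test or threshold attached, and even severe assumptions move it far less than its sampling error. Last-contact censoring is also a common convention in a single-arm pilot.

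All of this limits the size of the point. It does not remove it: a censoring rule matters precisely when the schedule is not kept, and this one allows unexamined time to count.

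Two stronger readings are not supported. A reader might infer that the 5-year rate will be too high. That requires both contact after the last exam and unreported progression in the gap, and the documents establish neither. A reader might also take the 20% accrual inflation in Section 12 as the plan's estimate of call-only patients. That allowance covers patients who are unevaluable or lost. A patient who is truly lost has no later contact, so the mechanism does not touch her. The 20% in the working is a free assumption.

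**Conclusion.** The point holds as a conditional one. The rule in 12.2.2 can credit unexamined time as progression-free, and where progression in that time goes unreported the error is upward. At a true rate of 80%, plausible scenarios give about 0 to 2 points and extreme ones about 4; at 70% the extreme is about 6. The Greenwood interval can also be somewhat too narrow, by about 12% in the worked case. These sizes rest on assumed call-only shares, gap lengths, detection by call and a constant hazard, none of which the documents supply. The bias is about zero if exams are kept or calls elicit recurrence, and it is well inside the half-width of about 14 points per cohort. This is a cheap improvement to a secondary, descriptive endpoint. It has no bearing on the feasibility decision.

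**What to change.** In 12.2.2, replace the date of last contact with the date of the last disease evaluation (clinical exam or imaging) showing no progression. Keep death from any cause as an event, and align the definition in 8.1.2 with it.

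State in advance one rule for progressions or deaths first learned of after missed exams. The rule should say whether such events count and on what date. If they count, it should acknowledge the downward bias that follows when other patients are censored at last exam (step 5 of the working). A rule that censors deaths falling too long after the last exam is not needed here and would change the endpoint that 12.2.2 defines.

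Report the last-contact version as a sensitivity analysis. If the two curves agree, the question is closed.

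The cost is a few sentences. The exams are already scheduled, so no new data are needed. The price is slightly less follow-up time and a slightly wider interval.
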